**Aim2: Examine long-term benefit of daily home use of lower electrical stimulation (long-term benefit):** Eligible participants will be randomized (ratio: 1:1) to either active (active group, n=20) or sham (sham group, n=20) therapy group. After receiving education, both groups will receive a home-based electrical stimulation system (Tennant Biomodulator device) for daily use at home up to 4 weeks. The duration of each treatment session per day will be one hour. The active group will receive an active electrical stimulation device. The control group will receive an identical device but without active electrical stimulation output. Participants and physicians who are treating the wound would be blinded to the type of device assignment. The study coordinator will be aware of assignment (active device or sham device). Each unit will be coded with a unique identification number. At the last visit, the study coordinator will reveal their group allocation. Since participating patients will have moderate-to-severe peripheral sensory neuropathy, they will be unable to determine via “feeling” whether or not they were receiving electrical stimulation. Patients will visit the clinic on weekly basis up to 4 weeks for assessing outcomes. The primary outcomes include changes in speed of wound healing and changes in plantar sensation. Secondary outcomes include patients self-report outcomes (e.g., pain, sleep quality, and quality of life), changes in mobility (e.g. physical activities and gait), and adverse outcomes (e.g., infection, amputation, etc.). Skin perfusion will be assessed similar to the method described in the Aim 1. Plantar sensation will be assessed using vibratory

perception threshold. Balance will be assessed using wearable sensors (BalanSENS, Biosensics LLC, MA, USA), mobility will be assessed using wearable sensors (PAMSys, Biosensics LLC, MA, USA), sleep quality will be assessed using PSQI questionnaire, and quality of life will be assessed using PROMIS Global.

Our hypotheses are

*H2:* Weekly speed of wound healing would be higher in the active group compared to the shame group

*H3:* Plantar sensation is improving in the active group in response to active therapy.

*H4:* Patient-reported outcomes and other secondary outcomes will be improved in the active group.

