### **Sample size estimation:**

The estimated number of study subjects is 40. The sample size for the short-term effect (immediate changes in skin perfusion) was estimated to achieve 85% power when comparing to baseline values, using assumed rates of 50% and 10% improvement, respectively. A two-sided test of results in evaluable subjects (qualified for analyses of efficacy on immediate changes on skin perfusion) will provide the specified power at a 5% significance level. Sample size calculations resulted in a requirement for a total of 27 subjects. The sample size for long term benefit was estimated based on our previous study (Najafi et al, Diabetes Sci & Tech, 2017) in which effectiveness of daily use of electrical stimulation to improve balance was examined using a randomized controlled trial model. An effect size of greater than Cohen’s  $d=1.35$  was observed for improvement of mobility post plantar electrical stimulation intervention. In this study we will use a power of 80%, two –tailed t-test, and alpha level of 5% to observe a significant improvement in the intervention group receiving active stimulation compared to sham group (with nonfunctional stimulator), 18 subjects per group is required. Assuming a 10% drop out, the estimated sample size would be 20 subjects per arm. We recognize that this sample size may not be sufficient to validate all primary and secondary outcomes, but would be sufficient to estimate trend and estimate the sample size for follow up study. Upon approval of the sponsor, availability of budget, and based on initial results (first 20 subjects), the sample size may be increased as well.

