Gram Stain: Bacteria levels will be assessed by collecting a samples and ordering a Gram Stain assessment, which provides an estimate of number of bacteria in the wound. A sample will be collecting before treatment and at 4 weeks.

Wound photo: A digital photo/video will be taken to record wound size.

Thermal Image: A Thermal camera will be used to obtain an image of the wound and observe inflammation.

Definition of Healed Wounds: A wound will be considered “healed” when it is fully epithelialized with no drainage. Only patients with non-infected wound will be recruited. *Infection* will be defined as a patient with three of six clinical signs of infection (erythema, heat, edema, pain, loss of function, purulence) or leukocytosis. We will use the Infectious Diseases Society of America’s Diabetic Foot Infection guidelines to stratify the severity of infection. This guideline stratifies infections into four categories (none, mild, moderate, and severe) based on practical clinical and laboratory findings. Our group has shown this system to be predictive of morbidity.

Health Questionnaires: Quality of Life, Frailty Status, Fear of Falling, Sleep Quality, Depression and Mental Status and Device Acceptability: To evaluate functional status we will use well-accepted questionnaires, PROMIS for Quality of Life, Sleep Quality questionnaire (PSQI), MOCA for cognitive assessment, FES-I for fear of falling, CES-D for depression and TSFI for frailty status. During the last visit, we will ask an acceptability questionnaire.

Upper Extremity Assessment: Investigators will measure the participant's arm motion using a wearable sensor (LegSys, Biosensics LLC, MA USA). This sensor will be placed around the wrist. While being at a comfortable position, the participant will be asked to flex and extend their arm for 20 seconds at a fast speed. They will also be asked to repeat this task but counting backwards as the participants flex and extend their arm (dual task). (Measurement will be done at baseline and visit 4)

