**Title: ELECTRICAL STIMULATION AS AN ADJUNCTIVE THERAPY TO ACCELERATE WOUND HEALING
IN PEOPLE WITH PERIPHERAL ARTERIAL DISEASE AND PLANTAR ULCERS & A RANDOMIZED
CONTROLLED TRIAL**

Identifier: NCT03821675

Date: 10/8/2021

Statistical analysis plan

Continuous data were reported with mean \pm standard deviation (SD). Categorical data were presented as count (%). Shapiro-Wilk test was conducted to identify the normal distribution of continuous variables. One-way ANOVA for normally distributed variables or Mann-Whitney U test for non-normally distributed variables was used to estimate differences of mean between control and intervention groups. χ^2 test was used to determine significant level between the groups for categorical variables. The effect size was measured using OR and 95% CI for categorical variables, and Cohen's d to discriminate the difference of primary and secondary outcomes between groups. Outcome changes were assessed over time compared to BL within (ie, time effect) and between (ie, time \times group effect) groups using linear mixed model for normally distributed outcome and generalized estimating equations for non-normally distributed outcome with adjustment for potential confounders. Least significant difference method was used for multiple pairwise comparisons. Pearson and Spearman correlation analysis were performed to assess the relationship between wound or demographics/clinical characteristics, and vascular outcomes. The level of statistical significance was set at $P < .050$. To detect changes in perfusion in individuals with marked limb ischemia, a sub-analysis of patients with moderate to severe peripheral arterial disease (PAD) (ABI < 0.8 or > 1.4 at BL)²⁴ was performed. To detect associated risk comorbidities influencing wound healing in those healers (defined as $\geq 50\%$ of area reduction)²⁵ vs non healers under E-stim, a sub-analysis in the IG was also performed.

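### The healer v non-healer comparison is confined to the active arm, so it cannot separate general prognosis from a changed device effect, and as a prognostic analysis it is inefficient

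*SAP*

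**What the plan says.** The last sentence of the SAP sets out a sub-analysis whose aim is given as "To detect associated risk comorbidities influencing wound healing in those healers". Healers are "defined as $\geq 50\%$ of area reduction", and they are compared with the remaining patients of the same arm: "vs non healers under E-stim, a sub-analysis in the IG was also performed". For this sub-analysis the SAP names no sham-arm counterpart, no arm by factor term, no list of comorbidities, no time point for the 50% cut and no multiplicity control. The only multiplicity method in the SAP is least significant difference, for pairwise comparisons.

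The protocol does not mention this sub-analysis. Under Study Design, Aim 2, patients are "randomized (ratio: 1:1) to either active (active group, n=20) or sham (sham group, n=20) therapy group". Under Study Tasks a wound counts as healed "when it is fully epithelialized with no drainage", which is a different and stricter state than the SAP's healer category.

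**The concern.** Two questions could lie behind the sub-analysis, and the plan suits neither.

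- **Who heals because of stimulation?** This is a question about effect modification and needs the sham arm. If patients with, say, low albumin heal poorly on the device, only the sham patients can show whether they would have healed just as poorly without it.
- **Who heals, among patients like these?** This is prognosis. Nothing is gained by leaving out the sham patients or by reducing a continuous outcome to yes/no, and both cost power.

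At stake is how the resulting list of comorbidities is understood. The SAP's reference to non-healers on stimulation makes it easy to read the list as saying who does and does not benefit from the device. The analysis could not support that.

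**Working it through.** **Inputs from the documents.** Allocation is 1:1 with 20 per arm (protocol, Study Design). The protocol's Sample size estimation section says "18 subjects per group is required", and then "Assuming a 10% drop out, the estimated sample size would be 20 subjects per arm". The significance level is 0.05 and the healer cut is 50% area reduction (SAP).

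**The plan's own figure.** The SAP gives no sample size or power for this sub-analysis, so there is none to reproduce. The dropout step reproduces: 18 / 0.9 = 20. I therefore use 20 per arm, and 18 as the evaluable number.

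**Assumptions, not in the documents.** The healer share is 20% to 50%. The outcome underlying the cut is roughly normal. The factor is continuous, with correlation 0.3 to 0.5 with healing.

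**1. Loss from the cut.** The information retained when a normal outcome is cut so that a share p are healers is φ(z_p)² / [p(1 − p)].

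| Healer share | Calculation | Retained | Lost | Retained with half the sample |
|---|---|---|---|---|
| 50% | 0.3989² / 0.25 | 64% | 36% | 32% |
| 30% | 0.3477² / 0.21 | 58% | 42% | 29% |
| 20% | 0.2800² / 0.16 | 49% | 51% | 25% |

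The last column also counts the omitted sham arm. It applies only when the target is prognosis.

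**2. What the active arm alone can detect.** For a two-sample t-test at 80% power and two-sided 5%, the detectable difference between healers and non-healers is d = 1.32 (10 v 10), 1.45 (6 v 14) or 1.66 (4 v 16). With 18 patients it is 1.41 to 1.69. A yes/no comorbidity present in 30% v 60% of 10 v 10 patients has 12% power by Fisher's exact test. If ten independent comorbidities with no true effect were tested at 0.05 (an assumed number), the chance of at least one false positive is 1 − 0.95¹⁰ = 40%.

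**3. Simulation of a purely prognostic factor.** The slope is the same in both arms, with no interaction, 20 per arm and healers split at the median. Entries are the share of trials with p < 0.05.

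| Correlation | Active arm only, healer v non-healer | Two-arm additive model, continuous | Arm by factor interaction |
|---|---|---|---|
| 0.3 | about 16–17% | 46% | 5% |
| 0.4 | 27% | 73% | 5% |
| 0.5 | 43% | 92% | 5% |

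With 18 per arm and correlation 0.4, the first two figures are about 26% and 67%. Both columns are power to find a real association with healing; they are not error rates. The 5% is the nominal level of the interaction test, as expected when there is no interaction.

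**4. Which coefficient to report.** If arm is coded 0/1 and the interaction is in the model, the factor coefficient is the slope in the sham arm only. Its power is about 27% / 45% / 66% at correlations 0.3 / 0.4 / 0.5. The gain in step 3 needs the additive model or centred arm coding.

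**5. What the interaction can show.** The standard error of a difference in slopes is about √(2/n) in SD units. The slope difference detectable at 80% power is (1.96 + 0.84) × √(2/20) = 0.89 SD per SD of the factor, or (1.96 + 0.84) × √(2/18) = 0.93 with 18 per arm. If the factor acts only in the active arm at correlation 0.4, the interaction has about 23% power.

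**The case against.** The strongest defence is that the SAP's stated target is comorbidities related to wound healing, in patients who happen to be treated. It does not promise a list of device responders. As a description of prognosis among treated patients the comparison is valid, though weak. It is one of two closing sub-analyses, and the outcome changes themselves go into a two-arm mixed model or GEE with a time by group effect, where the 50% cut plays no part. The replacement is no cure either, because an interaction with 20 per arm has little power. Finally, many comorbidities are yes/no, so power figures for a continuous factor flatter every method.

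Most of this stands, and it rules out three stronger readings that a reader might infer:

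- **That the findings will be reported as response to the device.** The SAP commits to no such interpretation; its wording permits it and the analysis cannot exclude it.
- **That most of the information is lost through the 50% cut.** The cut alone loses 36% at an even split and passes one half only near a 20% healer share (or, by symmetry, 80%). Most is lost only when the missing sham arm is also counted and the target is prognosis.
- **That the 27% is a false-positive rate.** It is the chance of detecting an association that is real.

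It is also possible to infer that the list would steer patient selection in a later study. The protocol speaks of estimating a trend and the sample size for a follow-up study; it says nothing of selecting patients by comorbidity.

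What the defence does not answer is why the sham patients are left out. Under the prognostic reading, their omission has no benefit.

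**Conclusion.** The point holds in limited form. An active-arm-only comparison cannot tell a general predictor of healing from a modifier of the device effect; this follows from the design and depends on no assumption. As a prognostic analysis it is inefficient: 36% to 51% of the information goes with the cut, half the sample goes with the sham arm, and power at correlation 0.4 is about 27% where about 73% was available (about 26% v 67% with 18 per arm).

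The sizes rest on an assumed healer share, an approximately normal outcome and a continuous factor. For yes/no comorbidities power would be lower. The defect is confined to one sub-analysis that should be read as exploratory. The primary outcomes and the main between-arm comparison are untouched.

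**What to change.** 1. In all randomised patients, model continuous percent area reduction at week 4 on arm and factor. Take prognosis from this additive model, or from a model with centred arm coding.
2. Then add arm by factor. Make any device-specific statement only from that interaction, with its 95% CI.
3. Keep the 50% split as description, state its time point, and note that it is not the protocol's definition of a healed wound.
4. List the comorbidities examined, report how many were tested, and label the whole analysis exploratory.

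The cost is a few lines of SAP text and slightly more analysis. The protocol schedules medical history at baseline and wound photographs at baseline and each weekly visit, without distinction by arm, so no new data are needed. Since the SAP is written in the past tense, the analysis may need to be re-run, or at least relabelled as prognosis among treated patients. The interaction estimates will be wide, and the report should say so with the figures above, so that a null interaction is not taken as evidence that the device works equally well in everyone.
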